11.3 Handling of Missing Data

Data will be analyzed as recorded in the database. No imputation of missing values will be performed unless indicated otherwise.

12.0 DATA AND SAFETY MONITORING PLAN

Toxicity and accrual monitoring will be performed on a routine basis by the study investigators as well as the multidisciplinary members of the Amyloid Center at Boston University, which has over 40 years' experience in the treatment of AL amyloidosis. Subjects will undergo toxicity assessment, performance status assessment and laboratory tests before each dose. Response assessment will be conducted every three months. The clinical status and laboratory reports of the study participants will be reviewed routinely by treating physicians. Dose modifications/interruptions or discontinuation will be implemented according to Section 8.

In addition, a Medical Monitor will be assigned to the study. The Medical Monitor must be a qualified clinician with relevant expertise, but no direct connection with the research, whose primary responsibility is to provide independent safety monitoring in a timely fashion. The PI will submit a

report to the Medical Monitor, at a minimum of once every 6 months, including a list of all adverse events and serious adverse events (regardless of relatedness). In addition, any unanticipated problems involving risks to participants or others and participant deaths within 30 days of study intervention will be reported to the Medical Monitor within 48 hours. The Medical Monitor is expected to provide a formal, unbiased written report evaluating individual and cumulative participant safety data when making recommendations regarding continuation of the study. Although the PI is responsible for assigning causality, the medical monitor will comment on whether or not (s)he is in agreement. Medical Monitor reports will must be submitted to the PI following each review (at a minimum of once every 6 months), which the PI will, in turn, submit to the IRB. Although there is no pre-determined criteria for early termination due to toxicity, the Medical Monitor and investigators will evaluate toxicities on a continuing basis, and will terminate the study early if toxicities exceed acceptable parameters. Each individual situation will be reviewed, and response data will be considered. The study will be stopped early if it appears that the benefit no longer outweighs the risks.

12.1 Interventional IIS Janssen Scientific Affairs Requirements for Safety Data Collection and Reporting

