12.1.3 Definitions

Adverse Event (AE)

An adverse event is any untoward medical occurrence in a clinical study subject administered a medicinal (investigational or non-investigational) product. An adverse event does not necessarily have a causal relationship with the treatment. An adverse event can therefore be

any unfavorable and unintended sign (including an abnormal finding), symptom, or disease temporally associated with the use of a medicinal (investigational or non-investigational) product, whether or not related to that medicinal (investigational or non-investigational) product. (Definition per International Conference on Harmonisation [ICH])

This includes any occurrence that is new in onset or aggravated in severity or frequency from the baseline condition, or abnormal results of diagnostic procedures, including laboratory test abnormalities.

Adverse Events of Special Interest

Adverse events of special interest are events that Janssen Scientific Affairs, LLC is actively monitoring as a result of a previously identified signal (even if non-serious). These adverse events are:

- Infusion reactions: \geq grade 3
- Infections: \geq grade 4
- Cytopenias: \geq grade 4
- Tumor lysis syndrome
- Other malignancies
- Intravascular hemolysis – all grades

Any Adverse Event of Special Interest that is to be reported to the COMPANY should be recorded on a Serious Adverse Event Report Form and be reported to the COMPANY within 24 hours of knowledge of the event.

Individual Case Safety Report (ICSR)

A valid ICSR must contain the four minimum criteria required to meet regulatory reporting requirements.

- an identifiable subject (but not disclosing personal information such as the subject's name, initials or address)
- an identifiable reporter (investigational site)
- a Janssen medicinal product
- an adverse event, outcome, or certain special situations

The minimum information required is:

- suspected Janssen medicinal product (doses, indication)
- date of therapy (start and end date, if available)
- batch or lot number, if available
- subject details (subject ID and country)
- gender
- age at AE onset
- reporter ID
- adverse event detail (AE verbatim in English), onset date, relatedness, causality, action taken, outcome, (if available)
- Janssen protocol ID

Product Quality Complaint (PQC)

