12.1.8.1 SAEs, Adverse Events of special Interest and Special Reporting Situations

All serious adverse events that have not resolved by the end of the study, or that have not resolved upon discontinuation of the subject's participation in the study, must be followed until any of the following occurs:

- The event resolves
- The event stabilizes
- The event returns to baseline, if a baseline value/status is available
- The event can be attributed to agents other than the study drug or to factors unrelated to study conduct
- It becomes unlikely that any additional information can be obtained (subject or health care practitioner refusal to provide additional information, lost to follow-up after demonstration of due diligence with follow-up efforts)

The principal investigator will transmit all SAEs, Adverse Events of special interest and special situations following exposure to a Janssen product under study in a form provided by Janssen Scientific Affairs, LLC in accordance with Section 12.1.10, Transmission Methods, in English **within 24-hours of becoming aware of the event(s).**

All follow-up information for serious adverse events that are not resolved at the end of the study or by the time of patient withdrawal must be reported directly by the principal investigator, **within 24 hours becoming aware,** to Janssen Scientific Affairs, LLC using the Janssen Scientific Affairs, LLC Serious Adverse Event Report

All available clinical information relevant to the evaluation of a related SAE, serious ADR or special situation is required.

- The principal investigator is responsible for ensuring that these cases are complete and if not are promptly followed-up. A safety report is not considered complete until all clinical details needed to interpret the case are received. Reporting of follow-up information should follow the same timeline as initial reports.
- Copies of any and all relevant correspondences with regulatory authorities and ethics committees regarding any and all serious adverse events, irrespective of association with the Janssen Product under study, are to be provided to Janssen Scientific Affairs, LLC using a transmission method in Section 12.1.10 **within 24 hours of such report or correspondence being sent to applicable health authorities.**

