Appendix 14.1

SAE Assessment Form

Date: _____
Study #: **BMC IRB #H-35360; Janssen Protocol #54767414AMY2002**
Sponsor/Investigator: **[name]**

A PHASE I-II TRIAL OF DARATUMUMAB FOR THE
TREATMENT OF PATIENTS WITH AL AMYLOIDOSIS

PATIENT # _____ **EVENT(s):** _____ **DATE:** _____

In accordance with the CCTO Standard Operating Procedures, documentation from the PI is required to document the outcome of his/her review of the events outlined in the SAE Report referenced above. **Please check the boxes, as appropriate, below...**

The OHRP and the FDA regulations require that *unanticipated problems* be promptly reported to the IRB. So what exactly is an *unanticipated problem*? The guidances state that in order for any **incident, experience, or outcome** to be an *unanticipated problem*, it must meet **all three** of the following criteria (unless the event is considered to be “anticipated”):

1	YES ___ NO ___	Is the event unexpected? It is unexpected if it is not listed in the investigator brochure or is not listed at the specificity or severity that has been observed; or, if an investigator brochure is not available, is not consistent with the risk information described in the general investigational plan or elsewhere in the current application;
2	YES ___ NO ___	Is the event related or possibly related to participation in the research (in this guidance document possibly related means there is a reasonable possibility that the incident, experience, or outcome may have been caused by the procedures involved in the research); AND
3	YES ___ NO ___	Does the safety report suggest that the research places subjects or others at a greater risk of harm (including physical, psychological, economic, or social harm) than was previously known or recognized.

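### A serious event or Grade 3 infusion reaction that is not an unanticipated problem may reach the independent Medical Monitor up to 6 months later, though the company must have it within 24 hours

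*Combined protocol and SAP*

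**What the plan says.** Section 12.0 gives the Medical Monitor independent safety monitoring as the primary task, asks that it be timely, and says that the monitor and the investigators evaluate toxicity continually. It then sets out how data reach the monitor. The PI sends a "report to the Medical Monitor, at a minimum of once every 6 months, including a list of all adverse events and serious adverse events". A faster deadline of 48 hours applies to a narrower set: "any unanticipated problems involving risks to participants or others and participant deaths within 30 days of study intervention will be reported to the Medical Monitor". The same section says that there are no preset toxicity criteria for early termination.

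Appendix 14.1 defines an unanticipated problem: "it must meet all three of the following criteria". The three are unexpectedness, at least possible relatedness, and a suggestion of greater risk than was previously recognised. The first is worded "Is the event unexpected? It is unexpected if it is not listed in the investigator brochure", and it continues so that an event listed at a different specificity or severity also counts as unexpected.

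Reporting to the company runs on a different clock. Section 12.1.3 lists infusion reactions of Grade 3 or higher as events of special interest, and such an event "should be recorded on a Serious Adverse Event Report Form and be reported to the COMPANY within 24 hours of knowledge of the event". Section 12.1.8.1 adds: "The principal investigator will transmit all SAEs, Adverse Events of special interest and special situations following exposure to a Janssen product under study", again within 24 hours.

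Section 11.2 provides one further review by the monitor, with the study temporarily closed, once the first 5 patients have completed at least 3 doses.

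**The concern.** Infusion reactions are the primary endpoint (sections 1.0 and 11.3). The plan expects its one independent reviewer to work continually, but names no route or deadline that would bring that reviewer ordinary serious events or Grade 3 infusion reactions as they happen. The 48-hour route filters on whether each single event is new in kind or severity. A known type of reaction that occurs more often in AL amyloidosis than in myeloma could pass through that filter one case at a time. Because 12.0 sets no toxicity threshold after the interim, later safety decisions rest on judgement. The monitor is also asked to say whether he or she agrees with the PI's causality calls, which cannot be done for events not yet received.

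**Working it through.** The plan states the 6-month interval and does not derive it, so there is no calculated figure to reproduce. The check compares the reporting clocks and then sizes the interval.

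**1. The clocks**

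| Event | Company (12.1.3, 12.1.8.1) | Medical Monitor (12.0) |
|---|---|---|
| Death within 30 days of study intervention | 24 hours | 48 hours |
| Serious event meeting all three Appendix 14.1 criteria | 24 hours | 48 hours |
| Other non-fatal serious event | 24 hours | next PI report, at most 6 months |
| Infusion reaction of Grade 3 or higher, not an unanticipated problem | 24 hours, on a serious-event form | next PI report, at most 6 months |

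If reports came exactly 6 months apart and events fell evenly between them, the mean wait would be 6 / 2 = 3 months.

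**2. Which events fall in the slow rows**

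Expectedness is judged against the Investigator's Brochure (12.1.4, Appendix 14.1), which is not among the documents. Section 3.1b is the nearest guide. It describes severe bronchospasm, dyspnea, hypoxia and hypotension as known reactions, and pneumonia as a known serious event. It also reports no reactions of Grade 3 or higher after the first infusion and no Grade 4 events.

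- A Grade 3 first-infusion reaction of a kind and severity listed in the Brochure fails the first criterion and takes the slow route.
- A Grade 4 reaction, or a Grade 3 reaction at a later infusion, could be unexpected by severity. If it met the other two criteria, it would go within 48 hours.

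**3. What the interim covers**

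It covers 5 of 25 patients (20%) and 3 doses. The other 20 (80%) have only the routes in 12.0. With even accrual of 25 patients over 24 months (11.1), the gap between patients is 24 / 25 = 0.96 month. The fifth patient enters at 4 × 0.96 = 3.84 months and reaches dose 3 two weeks later (14 / 30.4 = 0.46 month). The interim therefore falls at about 4.3 months.

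**4. Exposure in one interval**

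New patients per 6 months = 25 / 24 × 6 = 6.25. On the section 7.0 schedule, a patient who starts just after a report is due 8 (weeks 1-8) + 8 (weeks 9-23, every 2 weeks) + 1 (week 25) = 17 infusions by week 26.

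**5. How often the gap would matter**

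Section 3.1b gives under 2% for each of the four severe reaction types. Summing them as a rough ceiling gives under 8%, or fewer than 6.25 × 0.08 = 0.5 patients per interval. The list may be incomplete and the data are from myeloma. The rate in AL amyloidosis is not given, so a range is assumed for the per-patient risk p of a Grade 3 or higher reaction, with 6 new patients:

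- At least one: 1 − (1 − p)^6
- Two or more: 1 − (1 − p)^6 − 6p(1 − p)^5

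| Assumed p | At least one | Two or more |
|---|---|---|
| 2% | 11% | 0.6% |
| 5% | 26% | 3.3% |
| 10% | 47% | 11% |
| 20% | 74% | 34% |

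A cluster within one interval is unlikely at myeloma-like rates. It becomes plausible only if AL patients tolerate infusion clearly worse.

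**The case against.** The strongest case against is that the two clocks serve different purposes. Company reporting follows the company's own safety requirements, while the monitor carries out a cumulative review in an open-label, single-arm trial of an approved dose with no hypothesis test. Six months is the longest permitted gap, and more frequent reports are allowed. The 11.2 review covers early infusions, and section 8.0 sets rules for each patient's reactions that do not depend on the monitor. All of this stands. It means that the difference in clocks is not in itself an error and that no estimate changes.

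It does not supply the missing route. The wording about continuing evaluation comes with no data flow, and 11.2 stops at 5 patients.

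Four stronger readings are tempting, and the documents do not support them:

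- *Every Grade 3 infusion reaction is expected and so misses the 48-hour notice.* The severity clause in Appendix 14.1 and the unseen Brochure rule out so flat a statement.
- *Only the treating investigators see these events in real time.* Section 12.0 also names members of the Amyloid Center as routine monitors, and the company is told within 24 hours. The fair statement is that 12.0 describes only the Medical Monitor as independent.
- *The monitor receives the same form late.* The monitor is promised a list within the PI's report. The serious-event form goes to the company.
- *The 46% first-infusion rate measures the risk.* That figure is for any grade, whereas this point concerns Grade 3 or higher.

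**Conclusion.** The point holds in a limited form. For non-fatal serious events and Grade 3 infusion reactions that do not meet all three Appendix 14.1 criteria, the plan permits up to 6 months before the independent monitor must be told, against 24 hours for the company. This sits poorly with the timely and continuing role that 12.0 assigns to the monitor. After the interim it applies to 20 of 25 patients, with about 6 new starters per interval.

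The size rests on even accrual, on reports sent no more often than required, and on the Brochure listing at least some first-infusion reactions at Grade 3. Severe reactions are expected to be uncommon, so the change is a low-cost safeguard against an unexpected cluster in AL amyloidosis. It does not correct a defect in the analysis, and nothing here shows that such a cluster is likely.

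**What to change.** Amend the 48-hour sentence in section 12.0 so that each serious adverse event report and each special-interest report sent to the company under 12.1.8.1 is copied to the Medical Monitor at the same time. Leave the 48-hour notice for unanticipated problems and deaths as it is, and keep the 6-monthly cumulative report, which serves a different purpose.

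The cost is one sentence and one added recipient on reports already due within 24 hours. The downside is more messages for the monitor to read. No treatment rule, endpoint or analysis changes.

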12.1.1 OVERVIEW

As the sponsor of the Study, the principal investigator shall be solely responsible for complying, within the required timelines, any safety reporting obligation to competent Health Authorities, IRB/ECs and any participating (co or sub) investigators, as defined in applicable laws and regulations. For the purposes of this section, safety data includes adverse events, product quality complaints (PQCs), and special situations including pregnancies.

The principal investigator will provide safety information to Janssen Scientific Affairs, LLC on adverse events, special situations including pregnancies and product quality complaints as defined within this section.

12.1.2 Management of Safety Data

This Study has been designated as an interventional study. As such, all adverse events for Janssen Medicinal Products regardless of causality and special situations excluding those from subjects not exposed to a Janssen Medicinal Product and product quality complaints with or without an adverse event as described in this section will be reported from the time a subject has signed and dated an Informed Consent Form (ICF) until completion of the subject's last study-related procedure (which may include contact for follow-up safety). Serious adverse events will be reported for 30 days after the last dose of study drug.

For the purposes of this study, the Janssen medicinal product is: DARZALEX™
(daratumumab)

12.1.3 Definitions

Adverse Event (AE)

An adverse event is any untoward medical occurrence in a clinical study subject administered a medicinal (investigational or non-investigational) product. An adverse event does not necessarily have a causal relationship with the treatment. An adverse event can therefore be

any unfavorable and unintended sign (including an abnormal finding), symptom, or disease temporally associated with the use of a medicinal (investigational or non-investigational) product, whether or not related to that medicinal (investigational or non-investigational) product. (Definition per International Conference on Harmonisation [ICH])

This includes any occurrence that is new in onset or aggravated in severity or frequency from the baseline condition, or abnormal results of diagnostic procedures, including laboratory test abnormalities.

Adverse Events of Special Interest

Adverse events of special interest are events that Janssen Scientific Affairs, LLC is actively monitoring as a result of a previously identified signal (even if non-serious). These adverse events are:

- Infusion reactions: \geq grade 3
- Infections: \geq grade 4
- Cytopenias: \geq grade 4
- Tumor lysis syndrome
- Other malignancies
- Intravascular hemolysis – all grades

Any Adverse Event of Special Interest that is to be reported to the COMPANY should be recorded on a Serious Adverse Event Report Form and be reported to the COMPANY within 24 hours of knowledge of the event.

Individual Case Safety Report (ICSR)

A valid ICSR must contain the four minimum criteria required to meet regulatory reporting requirements.

- an identifiable subject (but not disclosing personal information such as the subject's name, initials or address)
- an identifiable reporter (investigational site)
- a Janssen medicinal product
- an adverse event, outcome, or certain special situations

The minimum information required is:

- suspected Janssen medicinal product (doses, indication)
- date of therapy (start and end date, if available)
- batch or lot number, if available
- subject details (subject ID and country)
- gender
- age at AE onset
- reporter ID
- adverse event detail (AE verbatim in English), onset date, relatedness, causality, action taken, outcome, (if available)
- Janssen protocol ID

Product Quality Complaint (PQC)

A product quality compliant is defined as any suspicion of a product defect related to a potential quality issue during manufacturing, packaging, release testing, stability monitoring, dose preparation, storage or distribution of the product, or delivery system. Not all PQC's involve a subject. Lot and batch numbers are of high significance and need to be collected whenever available.

Examples of PQC include but not limited to:

- Functional Problem: e.g., altered delivery rate in a controlled release product
- Physical Defect: e.g. abnormal odor, broken or crushed tablets/capsules
- Potential Dosing Device Malfunction: e.g., autoinjector button not working, needle detaching from syringe
- Suspected Contamination
- Suspected Counterfeit

Serious Adverse Event (SAE)

A serious adverse event based on ICH and EU Guidelines on Pharmacovigilance for Medicinal Products for Human Use is any untoward medical occurrence that at any dose:

- Results in death
- Is life-threatening
(The subject was at risk of death at the time of the event. It does not refer to an event that hypothetically might have caused death if it were more severe.)
- Requires inpatient hospitalization or prolongation of existing hospitalization
- Results in persistent or significant disability/incapacity
- Is a congenital anomaly/birth defect
- Is a suspected transmission of any infectious agent via a medicinal product
- Is medically important*

*Medical and scientific judgment should be exercised in deciding whether expedited reporting is also appropriate in other situations, such as important medical events that may not be immediately life threatening or result in death or hospitalization but may jeopardize the subject or may require intervention to prevent one of the other outcomes listed in the definition above. These should usually be considered serious.

NOTE: DEATH FOR ANY REASON SHOULD BE REPORTED AS A SERIOUS ADVERSE EVENT.

- **Hospitalization**

For reports of hospitalization, it is the sign, symptom or diagnosis which led to the hospitalization that is the serious event for which details must be provided.

Any event requiring hospitalization or prolongation of hospitalization that occurs during the study must be reported as a serious adverse event, except hospitalizations for the following:

- Hospitalizations not intended to treat an acute illness or adverse event (e.g., social reasons such as pending placement in long-term care facility)
- Surgery or procedure planned before entry into the study. [Note: Hospitalizations that were planned before the start of data collection and where the underlying condition for which the hospitalization was planned has not worsened will not be considered serious

adverse events. Any adverse event that results in a prolongation of the originally planned hospitalization is to be reported as a new serious adverse event.]

- [For convenience the investigator may choose to hospitalize the subject for the duration of the treatment period.]
- **Life-Threatening Conditions**
Disease progression should not be recorded as an adverse event or serious adverse event term; instead, signs and symptoms of clinical sequelae resulting from disease progression/lack of efficacy will be reported if they fulfill the serious adverse event definition.

